### 3. GENERAL INFORMATION

Objective	
The objective of the current study is to prospectively evaluate 3-month clinical outcomes from LASIK performed using the Phorcides surgical planning software with Contoura topography-guided ablation in both eyes of subjects with myopia and myopic astigmatism seeking refractive surgery for distance correction. Data will be compared to published results for wavefront optimized LASIK and LASIK performed with Contoura using other refractive algorithms.
 
The hypothesis is that use of the Phorcides planning software will result in a higher percentage of eyes with residual refractive cylinder <math>\leq 0.25D</math> than will be achieved with wavefront-optimized (WFO) LASIK. It is also expected that unaided postoperative visual acuity and visual symptoms will be improved.

Test Article(s)	Phorcides Analytical Engine refractive surgery planning software
Control Article(s)	None
Sample size	140 eyes of 70 subjects
Study Population	Subjects $\geq 20$ years of age with myopia and myopic astigmatism, who are suitable candidates for LASIK, meet the approved range of treatment for Contoura topography-guided LASIK and desire optimal uncorrected distance visual acuity in both eyes.
Number of sites	Four
Study Design	Prospective, single arm, open-label study.
Masking	None
Variables	Primary: 

● Residual refractive cylinder

 Secondary: 

● Monocular uncorrected distance visual acuity

- Monocular corrected distance visual acuity
- Residual refractive sphere
- Corneal aberrations
- Ocular aberrations (at sites equipped for such measurement)
- Subjective questionnaire evaluating visual symptoms such as light sensitivity glare, halos, and starbursts

Duration / Follow-up    Preoperative to 3 months postoperative

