## 5. INTRODUCTION

The Contoura software for the Alcon WaveLight excimer laser was approved several years ago, but some surgeons are unsure about how to plan treatments when the manifest cylinder determined by refraction differs significantly from the Contoura-derived cylinder. This has caused some surgeons to abandon the Contoura procedure. The Phorcides Analytical Engine (Phorcides) refractive surgical planning software has demonstrated efficacy in addressing this issue. Use of the Phorcides software is expected to simplify surgical planning and improve overall outcomes with topography-guided ablations; as a result, it may increase use of Contoura in clinical practice.

It is expected that clinical refractive outcomes with Phorcides will be superior to those obtained with wavefront-optimized refractive surgery using the same laser that have been reported in the literature. It is also expected that results with Phorcides will be superior to, and more consistent than, Contoura results reported in the literature that were based on alternative algorithms.

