## 6. OBJECTIVE

The objective of the study is to prospectively compare 3-month clinical outcomes of LASIK performed using the Phorcides surgical planning software with Contoura topography-guided ablation to wavefront-optimized (WFO) LASIK results and Contoura results based on other algorithms reported in the literature.

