### 7.2. Inclusion Criteria

Subjects are eligible for the study if they meet the following criteria:

**Note:** Ocular criteria must be met in both eyes.

- Candidate for Contoura excimer laser vision correction
- Gender: males and females.

- Age: 20 or older
- Willing and able to provide written informed consent for participation in the study.
- Willing and able to comply with scheduled visits and other study procedures.
- Good ocular health, with no pathology that compromises visual acuity (other than refractive error)
- Corrected preoperative visual acuity of 20/20 (0.0 logMAR) or better in the eye being treated
- Meet Contoura eligibility requirements (approved range): up to -8.00 D sphere, up to -3.00 D cylinder, and a spherical equivalent no greater than -9.00 D
- Desire good vision at distance in both eyes

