## **8. STUDY DESIGN**

The study is a prospective, single-arm open clinical trial to evaluate residual refractive error and distance visual acuity after excimer laser treatment for the correction of refractive error to produce good uncorrected distance vision. All eyes enrolled will have surgery planned with Phorcides and treated using the Contoura topography-guided surgery algorithm.

Subjects will be assessed pre-operatively and at 1 day, 1 month and 3 months post-operatively.

Clinical evaluations at 1 month and 3 months will include measurement of uncorrected distance visual acuity (UCDVA), manifest refraction, and corrected distance visual acuity (CDVA). At 3 months, corneal aberrations will be measured, and subjects will complete a questionnaire evaluating satisfaction with their visual outcome, quality of vision, and visual symptoms (light sensitivity, difficulty driving at night, reading difficulty, fluctuation in vision, glare, halos, and starbursts).

The primary outcome measure will be the residual refractive cylinder.

Secondary outcome measures will be the following:

- Uncorrected distance visual acuity
- Residual sphere
- Corneal aberrations
- Ocular aberrations, at sites with the appropriate equipment to measure such.
- Satisfaction with the visual outcome, quality of vision, and visual symptoms (light sensitivity, difficulty driving at night, reading difficulty, fluctuation in vision, glare, halos, and starbursts).

Safety measures will be

- Change in corrected distance visual acuity
- Satisfaction with the visual outcome, quality of vision, and visual symptoms (light sensitivity, difficulty driving at night, reading difficulty, fluctuation in vision, glare, halos, and starbursts).

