### ***8.2. Methods Used to Minimize Bias***

This is a single-arm study with both eyes of any subject enrolled. Patients will not be pre-selected for study inclusion. Any eligible patient presenting for, and eligible for, binocular Contoura treatment may be invited to participate.

The measurement of the postoperative refraction and visual acuity will be conducted in a systematic fashion to minimize bias. Individuals conducting visual acuity measures will be refracted with the methodology used in the Early Treatment Diabetic Retinopathy Study, with the same level of encouragement to subjects. Subjective questions will be asked in a similar manner to all patients. Alternatively, at the discretion of the investigator, patients may be asked to complete the questionnaire themselves.

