#### 9.4.1. Manifest refraction

Perform a manifest refraction with a high contrast logMAR ETDRS chart under photopic lighting conditions ( $>85$  cd/m^2). Document refraction results with sphere, cylinder and axis readings using the ETDRS protocol. If uncorrected visual acuity is not improved by manifest refraction, use zero for sphere and cylinder and draw a line through the blank for the axis. All visual acuities should be recorded as letters read on the ETDRS chart.

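### No published comparator is fixed for the expected superiority over WFO LASIK and other Contoura algorithms, so it could be chosen after this study's rate is known

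*Combined protocol and SAP*

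**What the plan says.** Section 3 describes a "Prospective, single arm, open-label study" with no control article. Its hypothesis is comparative: a higher percentage of eyes at 0.25 D of residual cylinder or less than WFO LASIK achieves. The yardstick is the literature: "Data will be compared to published results for wavefront optimized LASIK and LASIK performed with Contoura using other refractive algorithms". Section 5 expects results "superior to those obtained with wavefront-optimized refractive surgery using the same laser that have been reported in the literature", and also expects to beat Contoura planned with other algorithms. Section 6 repeats the second comparator as "Contoura results based on other algorithms reported in the literature". Section 19.2 is softer and expects results at least equal to both.

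Section 8 states "The primary outcome measure will be the residual refractive cylinder". Section 10.2 offers descriptive statistics plus whatever tests suit the data, two-sided at 5%. Section 11 justifies the sample size by similarity to comparable published studies, which it does not name. The two listed references support the software and are not designated as the benchmark.

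On case mix, Section 7.2 admits eyes "up to -8.00 D sphere, up to -3.00 D cylinder, and a spherical equivalent no greater than -9.00 D", with no minimum cylinder, and Section 8.2 says "Patients will not be pre-selected for study inclusion". Cylinder is measured at Visit 1 (Table 9.3-2; Section 9.4.1: "Document refraction results with sphere, cylinder and axis readings using the ETDRS protocol"), but Section 10 specifies no analysis that uses it.

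**The concern.** A single arm can describe three-month outcomes. The difficulty lies in the comparative claim. Apart from the same-laser limit for WFO, nothing determines which published rate this study must beat, or with what sample size behind it. A plan that leaves this open allows the comparator to be settled after the study's own rate is known, and the type I error of the comparison is then no longer controlled.

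A crude contrast with a paper whose eyes had more preoperative cylinder could also favour Phorcides with no effect of the software, and the opposite mix could hide a real benefit. Finally, Sections 3 and 5 speak of superiority while Section 19.2 would accept equality, so the success criterion is itself unsettled.

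**Working it through.** **Inputs.** From the documents: 140 eyes of 70 subjects, 10% dropout, 126 evaluable eyes (Section 11), two-sided 5% (Section 10.2). The documents give no success rate, comparator size or cylinder mix, so all of those below are assumptions. Eyes are treated as independent unless stated.

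**1. The plan's own figure.** 140 × (1 − 0.10) = 126, which reproduces. The 140 cannot be derived, because no rate, effect size or power is given.

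**2. Which rate, and which n.** Take 104/126 = 82.5% and an exact two-sided binomial test against a fixed benchmark:
- 70%: p = 0.002
- 75%: p = 0.051
- 80%: p = 0.58

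Comparator size matters too. With 101/126 (80.2%) against a published 70%, a pooled two-proportion test gives p = 0.147 if the paper has 50 eyes and 0.023 if it has 500.

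**3. Late choice of paper, worst case.** Let this study and each of m papers have 126 eyes and a true rate of 75%. Use the lowest paper, with P(lowest ≥ y) = P(Y ≥ y)^m, and declare superiority if (pA − pB)/√{[pA(1−pA) + pB(1−pB)]/126} > 1.96. Exact enumeration gives:
- one paper named in advance: 2.6%
- lowest of 2: 4.7%
- lowest of 3: 6.4%
- lowest of 5: 9.3%

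**4. Case mix, no technique effect.** Success in low/mid/high preoperative cylinder is assumed to be 85/75/65%, 90/75/60% or 95/75/50%. With a 126-eye comparator and a crude two-sample CI, P(false superiority) = 1 − Φ(1.96 − d/SE).

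Example, modest mix at 90/75/60:
- here: 0.40×0.90 + 0.35×0.75 + 0.25×0.60 = 0.7725
- comparator: 0.30×0.90 + 0.35×0.75 + 0.35×0.60 = 0.7425
- d = 0.030, SE = √[(0.7725×0.2275 + 0.7425×0.2575)/126] = 0.0540
- 1 − Φ(1.96 − 0.556) = 8.0%

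Inter-eye correlation of 0.5 in both series multiplies both variances by 1.5. Ranges over the three gradients:

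| Mix here v comparator (low/mid/high, %) | Independent eyes | Correlation 0.5, both series |
|---|---|---|
| Slight: 35/35/30 v 30/35/35 | 4–6% | 4–5% |
| Modest: 40/35/25 v 30/35/35 | 6–13% | 5–10% |
| Large: 50/30/20 v 20/40/40 | 15–52% | 11–38% |

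The nominal figure is 2.5%. The bias can run the other way: at 90/75/60 with the mixes reversed, a true 7.5-point benefit would appear as 7.5 − 1.5 = 6.0, 7.5 − 3.0 = 4.5 or 7.5 − 7.5 = 0 points.

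**5. Precision after standardising** (90/75/60, modest mix). Half-width = 1.96√(V + V0).
- V = Σ wB² r(1−r)/(126 wA) = (0.02025 + 0.06563 + 0.11760)/126 = 0.001615
- V0 = 0.7425×0.2575/126 = 0.001517
- half-width = 1.96√0.003132 = 11.0 points, against 10.6 crude; for the large mix, 12.4 against 10.5
- with correlation 0.5 in this study only: 1.96√(1.5×0.001615 + 0.001517) = 12.3 points

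Power for a true 7.5-point benefit is Φ(7.5×1.96/half-width − 1.96): about 27% at 11.0 points and 22% at 12.3. Dropping V0 would give 1.96√0.001615 = 7.9 points and about 46%; the crude 10.6 gives about 28%. Most of the loss therefore comes from admitting the comparator's sampling error, and little from standardising.

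**The case against.** The strongest reply is that the plan sets no formal superiority rule. Sections 3 and 5 state a hypothesis and expectations, Section 10 is mainly descriptive, and a comparison with published results could mean the literature as a whole. Fitting tests to the data may refer only to data type or distribution. All of this is fair. A reader might infer that the sponsor intends to pick a favourable paper, but the documents do not say so; they only leave it possible. Picking the lowest paper is a worst case. The open-label design adds little, since masking would not prevent a late choice of publication.

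A reader might also infer that case-mix bias is certain. It requires success to fall as preoperative cylinder rises, and no passage says that it does. Testing against an error-free published rate would raise the large-mix figure at 90/75/60 from 29% to 48%, but that ignores the comparator's sampling error, and nothing in the documents supports so large an imbalance. Not pre-selecting patients is, moreover, a step against bias.

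Standardising on manifest cylinder would also leave unbalanced the one planning difficulty that Section 5 names, a discrepancy between manifest and Contoura-derived cylinder. What survives is the documentary gap: a superiority hypothesis whose comparator is not fixed, for WFO and for other Contoura algorithms alike.

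**Conclusion.** The concern holds for the comparative claims and leaves the descriptive results untouched. That no paper, selection rule, rate or n is fixed, and that no use of preoperative cylinder is planned, is documented. That the choice of benchmark could settle the conclusion follows from the arithmetic: the same 104/126 runs from p = 0.002 to 0.58 across benchmarks of 70% to 80%. The worst-case inflation from late selection is from 2.6% to between 4.7% and 9.3% for two to five equal papers. The case-mix contribution is plausible but assumed in both existence and size: small for slight or modest differences, substantial only for a large one. The change should be made before Visit 5 data are viewed, because a comparator named later cannot be shown to have been chosen independently of the result.

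**What to change.** Before any Visit 5 data are viewed:

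1. For the WFO comparison, and likewise for the other-Contoura comparison, name the publication(s) or a selection rule. Fix the rate of eyes at 0.25 D or less, the n, and the preoperative cylinder distribution with its stratum cut-points.
2. Where the chosen paper reports usable strata, directly standardise this study's Visit 5 rate to that distribution using the Visit 1 manifest cylinder, and report results by stratum.
3. Base any superiority statement on the two-sided 95% CI for that difference, with subject-clustered variance here and the comparator's sampling error included. Align Section 19.2 with this criterion.
4. Otherwise report a descriptive contrast without a superiority claim.
5. State that other differences remain unadjusted, including surgeon, era, refraction method and the discrepancy between manifest and Contoura-derived cylinder.

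The cost is SAP wording and a modest extra analysis of data already collected, with no new patients or visits. Feasibility of item 2 depends on what the chosen papers report. Under the large assumed mix, the high-cylinder stratum would have about 0.20 × 126 = 25 eyes but carry 40% of the weight. The sponsor should accept in advance that, at the precision shown above, a superiority claim would often not be supported even if a 7.5-point benefit were real.

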## 5. INTRODUCTION

The Contoura software for the Alcon WaveLight excimer laser was approved several years ago, but some surgeons are unsure about how to plan treatments when the manifest cylinder determined by refraction differs significantly from the Contoura-derived cylinder. This has caused some surgeons to abandon the Contoura procedure. The Phorcides Analytical Engine (Phorcides) refractive surgical planning software has demonstrated efficacy in addressing this issue. Use of the Phorcides software is expected to simplify surgical planning and improve overall outcomes with topography-guided ablations; as a result, it may increase use of Contoura in clinical practice.

It is expected that clinical refractive outcomes with Phorcides will be superior to those obtained with wavefront-optimized refractive surgery using the same laser that have been reported in the literature. It is also expected that results with Phorcides will be superior to, and more consistent than, Contoura results reported in the literature that were based on alternative algorithms.

## 6. OBJECTIVE

The objective of the study is to prospectively compare 3-month clinical outcomes of LASIK performed using the Phorcides surgical planning software with Contoura topography-guided ablation to wavefront-optimized (WFO) LASIK results and Contoura results based on other algorithms reported in the literature.

## 7. SUBJECTS

### 7.1. Subject Population

Eligible test subjects will be patients presenting for LASIK who meet the approved refractive range and clinical indications for topography-guided ablation. Both eyes must be eligible for treatment.

A total of 140 eyes of 70 subjects will be enrolled across four clinical sites. A minimum of 10 and a maximum of 25 subjects will be enrolled at any one site, based on speed of enrollment. Subjects must meet the inclusion criteria. Prior to enrollment, subjects will be provided information on the study and asked to sign a patient information and consent form to participate. The patient information and consent form will be approved by an appropriate ethics committee.

### 7.2. Inclusion Criteria

Subjects are eligible for the study if they meet the following criteria:

**Note:** Ocular criteria must be met in both eyes.

- Candidate for Contoura excimer laser vision correction
- Gender: males and females.

- Age: 20 or older
- Willing and able to provide written informed consent for participation in the study.
- Willing and able to comply with scheduled visits and other study procedures.
- Good ocular health, with no pathology that compromises visual acuity (other than refractive error)
- Corrected preoperative visual acuity of 20/20 (0.0 logMAR) or better in the eye being treated
- Meet Contoura eligibility requirements (approved range): up to -8.00 D sphere, up to -3.00 D cylinder, and a spherical equivalent no greater than -9.00 D
- Desire good vision at distance in both eyes

### **7.3. Exclusion Criteria**

If any of the following exclusion criteria are applicable to the subject or either eye, the subject should not be enrolled in the study.

- Corneal pathology (e.g. opacities, epithelial basement membrane dystrophy, Fuchs' dystrophy, etc.)
- Previous corneal surgery (e.g., radial keratotomy, corneal refractive surgery or corneal transplant, DSAEK, DMEK, lamellar keratoplasty)
- Previous anterior or posterior chamber surgery (e.g., vitrectomy, laser iridotomy)
- Desire for good uncorrected near vision in one or both eyes
- Participation in (or current participation) any investigational drug or device trial within the previous 30 days prior to the start date of this trial
- Unsuitability for the trial, in the opinion of the investigator, for any reason
- Pregnancy or desire to become pregnant during the trial

### **7.4. Exclusion Criteria during surgery**

The following exclusion criteria are applicable to the study eye during the study

- Intraoperative complications.

Any subject whose surgery has been aborted for either eye should immediately be discontinued from the study and an exit form completed for that subject. These subjects will be followed according to the clinic standard of care and monitored for safety, but their data will be excluded from the study efficacy analysis. All adverse events will be appropriately documented and reported.

Participants who are considered to be in a vulnerable population will not be enrolled into the study. Vulnerable populations include, but are not limited to, the following:

- Prisoners
- Nursing home residents
- Institutionalized individuals
- Mentally disabled and cognitively impaired individuals
- Sponsor employees and their family members
- Site employees and their family members that are directly or indirectly involved in the study
- Economically disadvantaged individuals
- Educationally disadvantaged individuals
- Adults who do are illiterate
- Subjects who are deaf or have a severe hearing disability
- Terminally ill individuals
- Individuals with life-threatening conditions

## **8. STUDY DESIGN**

The study is a prospective, single-arm open clinical trial to evaluate residual refractive error and distance visual acuity after excimer laser treatment for the correction of refractive error to produce good uncorrected distance vision. All eyes enrolled will have surgery planned with Phorcides and treated using the Contoura topography-guided surgery algorithm.

Subjects will be assessed pre-operatively and at 1 day, 1 month and 3 months post-operatively.

Clinical evaluations at 1 month and 3 months will include measurement of uncorrected distance visual acuity (UCDVA), manifest refraction, and corrected distance visual acuity (CDVA). At 3 months, corneal aberrations will be measured, and subjects will complete a questionnaire evaluating satisfaction with their visual outcome, quality of vision, and visual symptoms (light sensitivity, difficulty driving at night, reading difficulty, fluctuation in vision, glare, halos, and starbursts).

The primary outcome measure will be the residual refractive cylinder.

Secondary outcome measures will be the following:

- Uncorrected distance visual acuity
- Residual sphere
- Corneal aberrations
- Ocular aberrations, at sites with the appropriate equipment to measure such.
- Satisfaction with the visual outcome, quality of vision, and visual symptoms (light sensitivity, difficulty driving at night, reading difficulty, fluctuation in vision, glare, halos, and starbursts).

Safety measures will be

- Change in corrected distance visual acuity
- Satisfaction with the visual outcome, quality of vision, and visual symptoms (light sensitivity, difficulty driving at night, reading difficulty, fluctuation in vision, glare, halos, and starbursts).

### ***8.2. Methods Used to Minimize Bias***

This is a single-arm study with both eyes of any subject enrolled. Patients will not be pre-selected for study inclusion. Any eligible patient presenting for, and eligible for, binocular Contoura treatment may be invited to participate.

The measurement of the postoperative refraction and visual acuity will be conducted in a systematic fashion to minimize bias. Individuals conducting visual acuity measures will be refracted with the methodology used in the Early Treatment Diabetic Retinopathy Study, with the same level of encouragement to subjects. Subjective questions will be asked in a similar manner to all patients. Alternatively, at the discretion of the investigator, patients may be asked to complete the questionnaire themselves.

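### Section 8.2 says patients are not pre-selected, but its invitation rule is only permissive and no count of those left out is kept, so the intention is neither enforced nor auditable

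*Combined protocol and SAP*

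**What the plan says.** Section 8.2, the plan's section on minimizing bias, states an intention: "Patients will not be pre-selected for study inclusion". The rule that follows it is: "Any eligible patient presenting for, and eligible for, binocular Contoura treatment may be invited to participate".

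Three other parts of the combined protocol and SAP bear on who enters:

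- Section 7.3 lists as an exclusion: "Unsuitability for the trial, in the opinion of the investigator, for any reason". It asks for no record of the reason.
- Section 7.1 sets the site numbers: "A minimum of 10 and a maximum of 25 subjects will be enrolled at any one site, based on speed of enrollment". The total is 70 subjects (140 eyes) at four sites.
- Section 9.2 puts a complete examination, including refraction and topography, ahead of participation and consent.

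No section requires that all or consecutive eligible patients be invited, or that anyone count those eligible, invited, declined or not invited.

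Section 3 describes the design as "Prospective, single arm, open-label study" and the comparison as follows: "Data will be compared to published results for wavefront optimized LASIK and LASIK performed with Contoura using other refractive algorithms". The hypothesis concerns the share of eyes with residual cylinder at or below 0.25 D, relative to wavefront-optimized LASIK. Section 10.2 plans descriptive statistics and unspecified further tests. It does not mention case-mix adjustment.

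**The concern.** A statement that patients are not pre-selected protects the result only if a rule carries it out or a record allows it to be checked. Here the rule allows invitation without requiring it, the unsuitability exclusion is open-ended, and no record is kept of patients passed over.

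The investigator may also be well informed when deciding whom to invite. Section 5 identifies the difficult case as one where the refraction and the Contoura measurement give clearly different cylinder. Under 9.2, both refraction and topography can be known before the invitation. Section 7.2 limits cylinder to -3.00 D but sets no lower bound, so the proportion of low-cylinder eyes is left to chance or choice.

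In a randomised trial, uneven invitation would mainly affect generalisability, because both arms would draw on the same patients. In a single-arm study judged against the literature, it acts on one side of the comparison only. If harder eyes were invited less often, the primary percentage would rise with no change in how well the software works. The study would also say less about the eyes for which the software was designed.

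**Working it through.** **Plan's own figure.** Section 11 expects 10% dropout from 140 eyes: 140 × (1 − 0.10) = 126 eyes, which reproduces the stated 126. The plan gives no success rate, reference rate, effect size or power. Every rate below is therefore an assumption.

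**Gain if the least favourable patients are never invited.** Let *p* be the success rate in all eligible eyes, *f* the fraction not invited and *q* their success rate. The rate among those invited is (*p* − *f* × *q*) / (1 − *f*).

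- *p* = 0.80, *f* = 0.10, *q* = 0.50: (0.80 − 0.05) / 0.90 = 0.833, a gain of 3.3 points.
- *p* = 0.80, *f* = 0.20, *q* = 0.60: (0.80 − 0.12) / 0.80 = 0.850, a gain of 5.0 points.

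**Precision of the primary percentage at 80%.**

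- Independent eyes: 1.96 × √(0.80 × 0.20 / 126) = 0.070, or 7.0 points.
- Two eyes per subject with between-eye correlation ρ (assumed): multiply by √(1 + ρ).
  - ρ = 0.3: 7.0 × 1.140 = 8.0 points.
  - ρ = 0.8: 7.0 × 1.342 = 9.4 points.

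**Partial selection.** Suppose the overall rate is 60%, 70% or 80%, and 20% to 30% of eligible eyes are harder cases whose success rate is 20 to 30 points below that of the others.

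| Harder cases invited | Rise in observed rate | Chance of falsely finding superiority |
|---|---|---|
| As often as others | 0 | 2.0% to 2.2% |
| Half as often | 1.8 to 3.7 points | 5% to 17% |
| Never | 4 to 9 points | 14% to 78% |

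The last column supposes that the true rate equals a fixed reference rate, that the 126 eyes are independent, and that the success threshold has an upper-tail probability of at most 2.5%. The plan specifies no such test, so the column is illustrative. Its wide range shows how far the answer depends on the assumed degree of selection.

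**The case against.** The strongest reply is that 8.2 should be read as a whole. Its first sentence rules out pre-selection, and the next most naturally means that no eligible patient is barred. Picking favourable cases would then breach the protocol. That is a fair reading, and it removes any suggestion that the plan licenses case-picking. It leaves untouched the fact that a breach could not be seen.

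A reader might infer more than the documents support:

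- **That investigators will choose easy eyes, or that the comparison is already biased.** Nothing shows this. Net bias also depends on how the published series were recruited, which cannot be judged from these documents.
- **That the range of 10 to 25 subjects per site is evidence of selection.** Section 7.1 ties it to speed of enrolment, which does not point to case-picking.
- **That no later analysis could detect selection.** This is too strong. Table 9.3-2 has refraction and topography taken preoperatively, so the enrolled case mix can be described, stratified by cylinder and set beside published baselines where these are reported. What stays hidden is who was left out, and selection on features not recorded.

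Two further points stand. The 3 to 5 points rest on assumed rates and on complete omission of the worst patients, which supposes that poor outcomes can be predicted well. An investigator-opinion exclusion is a general discretion clause and need not be removed; its use needs to be recorded.

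**Conclusion.** The concern holds as a gap in enforcement and audit. The plan states the right intention, gives a rule that does not secure it, and keeps no record by which it could be checked.

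Under an assumed 80% success rate, never inviting the least favourable 10% or 20% of patients would add about 3 to 5 points. That is smaller than the sampling half-width of 7 points for independent eyes, or 8 to 9 points allowing for correlated fellow eyes. Unlike sampling error, however, it would run in one direction and would not shrink with more subjects. The size is illustrative, since the documents supply no rates. The conclusion about enforcement rests on the text alone and does not depend on it.

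Consecutive invitation with reported counts is a better method for this design and inexpensive, so the change should be made. It needs to be in place before enrolment starts, because missed invitations cannot be reliably reconstructed.

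**What to change.** Replace the invitation sentence in 8.2 with:

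> Consecutive patients who meet the eligibility criteria in 7.2 and 7.3 and are not barred by 7.4 will be invited at each site until the site maximum or the study total is reached, with places reserved so that each site can reach its minimum of 10.

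The reference to 7.4 is needed because that section bars vulnerable groups who might otherwise satisfy 7.2 and 7.3. The reservation is needed because 25 + 25 + 20 = 70 would fill the study with the fourth site at zero.

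At each site, keep an anonymous count of patients eligible, invited, declined, and excluded as unsuitable, with a reason category for the last group. It should hold no individual clinical data from people who have not consented, because 9.1 requires consent before any study data are collected. Report the counts by site with the primary result, next to the preoperative sphere and cylinder of the enrolled eyes.

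The cost is less freedom in recruitment and a little coordinator time. There are no added visits or procedures, and the sample size is unchanged.
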